**LIST OF ABBREVIATIONS AND RELEVANT DEFINITIONS**

ABR	ABR form, General Assessment and Registration form, is the application form that is required for submission to the accredited Ethics Committee (In Dutch, ABR = Algemene Beoordeling en Registratie)
AE	Adverse Event
AR	Adverse Reaction
CA	Competent Authority
CCMO	Central Committee on Research Involving Human Subjects; in Dutch: Centrale Commissie Mensgebonden Onderzoek
CTLA-4	Cytotoxic T-Lymphocyte-associated protein-4
CV	Curriculum Vitae
DSMB	Data Safety Monitoring Board
EU	European Union
EudraCT	European drug regulatory affairs Clinical Trials
FFPE	Formalin fixed-paraffin embedded
GCP	Good Clinical Practice
IB	Investigator's Brochure
IC	Informed Consent
IHC	Immunohistochemistry
IMP	Investigational Medicinal Product
IMPD	Investigational Medicinal Product Dossier
METC	Medical research ethics committee (MREC); in Dutch: medisch ethische toetsing commissie (METC)
PD-1	Programmed Death Receptor-1
PD-L1	Programmed Death Ligand 1
PK	Pharmacokinetic
ROI	Region-of-interest
(S)AE	(Serious) Adverse Event
SPC	Summary of Product Characteristics (in Dutch: officiële productinformatie IB1-tekst)
Sponsor	The sponsor is the party that commissions the organisation or performance of the research, for example a pharmaceutical company, academic hospital, scientific organisation or investigator. A party that provides funding for a study but does not commission it is not regarded as the sponsor, but referred to as a subsidising party.

**SUSAR** Suspected Unexpected Serious Adverse Reaction

**Wbp** Personal Data Protection Act (in Dutch: Wet Bescherming Persoonsgevens)

**WMO** Medical Research Involving Human Subjects Act (in Dutch: Wet Medisch-wetenschappelijk Onderzoek met Mensen)

**WOCBP** Women of child bearing potential

## 1. SUMMARY

**Rationale:** Clinical trials have shown efficacy of PD1/PD-L1 checkpoint inhibitors in multiple solid tumors, including melanoma. Whole body information with regard to target presence, drug kinetics and dynamics, as well as binding of PD-L1 targeting agents to the immune system cells is lacking. Molecular imaging of PD-L1 could lead to new insights on heterogeneity of PD-L1 expression in metastatic lesions and be of help in the prediction of response to PD1/PD-L1 inhibitors in a non-invasive manner.

**Primary objectives:**

Phase one: To assess the dynamics and kinetics of  $[^{18}\text{F}]$ PD-L1 in human subjects to establish optimal scan schedule.

Phase two: To validate the  $[^{18}\text{F}]$ PD-L1 PET tracer by association of PD-L1 tumor expression as determined on PET and PD-L1 expression as determined by immunohistochemistry and to assess the association between the radiological response to anti-PD1 treatment and PD-L1 expression as measured by PET scanning and by immunohistochemistry

**Secondary objectives:** To determine between-subject and within-subject variability in  $[^{18}\text{F}]$ PD-L1 uptake in melanoma and non-small cell lung cancer metastases

**Study design:** This is a feasibility study for the use of  $[^{18}\text{F}]$ PD-L1 as a PET tracer that will be conducted in a single center. The study consists of two phases. The aim of phase one is to provide pharmacokinetic information on the tracer and to determine the optimal time point for imaging. In the second phase the main study objective will be assessed.

**Study population:** The study population consists of patients diagnosed with metastatic melanoma or non-small cell lung cancer that are eligible for treatment with nivolumab, a PD-1 blocking monoclonal antibody. Patients must be at least 18 years of age. In total, a maximum of 15 patients will be included.

**Intervention (if applicable):** The main intervention of this study is a  $[^{18}\text{F}]$ PD-L1 PET scan. In both phase one and phase two a scan sequence will be performed both at baseline and 6 weeks after initiation of nivolumab treatment. The PET scans will be combined with either a low dose or diagnostic CT scan of chest, abdomen and pelvis and a MRI of the brain. In phase two, a biopsy of at least one accessible lesion will be performed to analyze PD-L1 expression using immunohistochemical staining after each PET scan.

**Main study parameters/endpoints:**

- Phase one: To determine the optimal schedule for performing  $[^{18}\text{F}]$ PD-L1 PET scans.

- Phase two: To assess the association of PD-L1 expression as measured by PD-L1 tracer uptake on PET with PD-L1 expression as measured by immunohistochemical (IHC) staining for PD-L1 of corresponding tumor lesions.

**Nature and extent of the burden and risks associated with participation, benefit and group relatedness:** The expected applied injected activity of [F]PD-L1 is 200 MBq, as is the case for most other F-labeled tracers. The radiation burden for a dose of 200 MBq is approximately 4.4 mSv. Patients will receive 2 serial PET scans each accompanied by a low dose CT scan which adds up to a total dose of 11.8 mSv. The radiation burden of these patients complies with category III (moderate risk) according to the International Commission on Radiological Protection (ICRP) guidelines (ICRP publication 62).

The biopsies needed in phase two of this study are obtained using an invasive procedure. Although biopsies are generally considered to be safe, they can be painful and carry certain risks, such as bleeding at the puncture site. Biopsies will preferably be taken from easily accessible lesions to minimize the burden and risk for the patient.

Whenever possible, all procedures that are part of the study protocol will be planned during regular visits to the hospital as part of care as usual.

## 2. INTRODUCTION AND RATIONALE

Melanoma is the most aggressive form of skin cancer. Its incidence has grown fast over the past few decades, with a current worldwide incidence rate of 121.000 and a mortality rate of 31.000 per year (1). In recent years important advancements have been made in the treatment of metastatic melanoma. One of these was the discovery that cancer could escape immune surveillance by expression of inhibitory immune checkpoint molecules, such as CTLA-4 and PD-1/PD-L1.

Lung cancer is the leading cause of cancer mortality worldwide for both men and women. The main risk factor for the development of NSCLC is smoking. In 2012 about 800 patients died of melanoma and over 10,000 people died of lung cancer in the Netherlands (2). During the last few years, important advancements have been made in the treatment of locally advanced and metastatic melanoma and NSCLC. One of them is the discovery and use of immune checkpoint inhibitors as successful therapy in these patients.

### 2.1 Immune checkpoint inhibition

For T cell activation two signals are necessary: binding of the antigen (AG) presented by the major histocompatibility complex to the T-cell receptor (TCR), and costimulatory signals from antigen-presenting cells (APCs) (3). Whereas co-stimulatory pathways will enhance T cell activation, proliferation and differentiation, so called co-inhibitory signaling pathways, such as the PD-1/PD-L1 axis, will counteract these effects (3,4). Upregulation of these so called checkpoint molecules promote attenuation of T cell activation (3). Under normal physiological circumstances, these mechanisms regulate tolerance by suppressing the immune response and thus protecting the body against self-reactive T cells and controlling inflammation within target organs. Tumors take advantage of these and other mechanisms to evade host immune responses and silence the immune system.(3,4-8) To overcome the functional unresponsiveness of the immune system and subsequently induce tumor regression, checkpoint inhibitors targeting CTLA-4, and more recently inhibitors targeting PD1/PD-L1, have been developed and successfully been tested in several solid tumor types with durable responses in a subset of patients (3).

### 2.2 PD1/PD-L1 blockade in melanoma and non-small cell lung cancer

Current first line therapy for patients with unresectable melanoma consists of treatment with anti-PD-1 immunoglobulines such as nivolumab (BMS-936558) or pembrolizumab (MK-3475). Both agents have shown an increase in overall survival in phase III studies, with preferable toxicity profiles as compared to other agents, such as the CTLA-4 inhibitor ipilimumab.

Data from the phase 1 trial for pembrolizumab showed a confirmed response rate in 38% of the patients (9). Objective response rate in a phase 2 trial of nivolumab was 32% (10). Nivolumab led to an even more durable response in patients with stage IV melanoma than ipilimumab, with a median overall survival of almost 17 months compared to 10 months with ipilimumab. In addition, the safety profile of nivolumab is better than that of ipilimumab, with fewer grade 3 or 4 adverse events.

Because of their different mode of action and different phase of T cell activation in which they play a role, combining nivolumab and ipilimumab has been explored in a clinical trial. This combination of CTLA-4 and PD1 blockade led to even higher objective response rates of up to 53%. Recently, this combination therapy has been approved in the Netherlands for the treatment in unresectable melanoma patients. However, the increase in response rates comes at the cost of more toxicity than either single agent (11).

Although efficacy data on immune checkpoint inhibitors are very promising, not all patients will benefit from these agents. Also, immune-related adverse events (irAEs), especially in combination therapy, can limit the use of immune modulating drugs. Key issues in the future of immunotherapy are the understanding of drug kinetics and dynamics in vivo, as well as the effects of these agents on the immune system, since these may be of help in the selection of patients that will benefit from checkpoint inhibiting therapy.

The objective response (ORR) rate of anti-PD-1 therapy in NSCLC varies based on histological subtype and PD-L1 expression of the tumor. For squamous cell and planocellular carcinoma with low PD-L1 expression ORR are 17% and 9% respectively (12,13). For low-PD-L1 adenocarcinoma, ORR is 8%. High PD-L1 expressing tumours show ORR rates of 30 to 45% (14, 15, 16).

between 19.4 – 42.5%, depending on PD-L1 expression (17). Compared to docetaxel, anti-PD-1 therapy showed prolonged survival (10.4 to 12.7 months vs. 8.5 months) (18). Overall, the treatment is well tolerated, with 9,5% adverse events of grade 3 or higher (17).Anti-PD-1 therapy was approved by the FDA for second line treatment of patients with high PD-L1 expressing NSCLC (>50 % based on IHC assay) in 2015 (16). Recently the indication was expanded to patients with tumors that express >=1% PD-L1 (18).

### 2.3 Molecular imaging with [18F]PD-L1

PD-L1 tumor surface expression, which is positive in 40-100% in metastatic melanoma, has been studied intensively as a potential biomarker for the selection of patients that qualify for anti-PD-1 therapy, but not without any obstacles. In early clinical trials, PD-L1 expression has been associated with response to PD1/PD-L1 inhibition (19-21). Later trials reported a response to PD1/PD-L1 checkpoint inhibitors in up to 47% of PD-L1-negative melanomas (22). Also, the potentially heterogeneous expression and fast dynamics of PD-L1 expression make clinical implementation

difficult (19). By labeling of a PD-L1 binding precursor with Fluoride-18 ( $^{18}\text{F}$ ), serial [ $^{18}\text{F}$ ]PD-L1-PET scanning can be used to assess whole body distribution, pharmacokinetics (PK) and pharmacodynamics (PD) and to relate findings to treatment effects. This could help in patient selection and possibly serve as an (early) biomarker for response to PD1/PD-L1 checkpoint inhibitors in the future.

In NSCLC PD-L1 expression is associated with response to therapy, as illustrated above. Therefore, identification of tumors with high PD-L1 expression in this patient category can be of high clinical value.

## 2.4 Rationale

Clinical trials have shown efficacy of PD1/PD-L1 checkpoint inhibitors in multiple solid tumors, including melanoma and NSCLC. Whole body information with regard to target presence, drug kinetics and dynamics, as well as binding of PD-L1 targeting agents to the immune system cells is lacking. Molecular imaging of PD-L1 could lead to new insights on heterogeneity of PD-L1 expression in metastatic lesions and be of help in the prediction of response to PD1/PD-L1 inhibitors in a non-invasive manner.

## 3. OBJECTIVES

### 3.1 Phase one

Primary Objective:

- To determine the optimal timing of imaging for [ $^{18}\text{F}$ ]PD-L1 tracer imaging of inoperable melanoma and NSCLC.

### 3.2 Phase two

Primary Objective:

- To assess the association of PD-L1 expression as measured by PD-L1 tracer uptake on PET and PD-L1 expression as measured by immunohistochemical (IHC) staining for PD-L1 of corresponding tumor lesions.
- To correlate response to anti-PD1 treatment with differences in tumor PD-L1 and PD1 expression between baseline and after 6 weeks of treatment, as quantified by PET and IHC analysis.

Secondary objectives:

- To characterize between-subject and within-subject variability in accumulation of the [F]PD-L1 tracer in melanoma and NSCLC metastases.

#### 4. STUDY DESIGN

This is a single center feasibility study for the application of [F]PD-L1 PET in patients with metastatic melanoma and NSCLC treated with anti-PD-1 therapy. The study will consist of a pharmacokinetics phase (phase one) and tracer validation phase (phase two). Phase one will be performed in a maximum of 5 patients. A [F]PD-L1 PET scan will be performed at baseline and six weeks after treatment initiation. Upon finishing phase one, the optimal time for tracer injection will be determined prior to the start of phase two. In phase two a [F]PD-L1 PET-CT scan will be performed in 10 patients at baseline and six weeks after treatment initiation. Also, a biopsy will be taken from at least one accessible tumor location after the PET-scan at baseline and the PET-scan after six weeks of therapy.

[figure not shown]

Fig.1 – General study overview.

#### 5. STUDY POPULATION

##### 5.1 Study population

All patients should be diagnosed with stage IV metastatic melanoma or non-small cell lung cancer. Patients should be eligible for treatment with nivolumab. Patients participating in other trials with this agent may participate in phase one of this study, as long as this does not interfere with either one of the study protocols. Patients participating in a clinical trial for nivolumab (e.g.: An open-label, single-arm, phase II, multicenter study to evaluate the efficacy of nivolumab in metastatic melanoma patients with symptomatic brain metastases) may participate in phase two of this study as well.

The University Medical Center Groningen (UMCG) is a referral center for metastatic melanoma. Yearly, approximately 100 patients start systemic treatment for metastatic melanoma in this study center, of which 30 are eligible for nivolumab therapy each year. Out of this group approximately 1-2 patients a month will be recruited for inclusion in this study.

### 5.3 Exclusion criteria

A potential subject who meets any of the following criteria will be excluded from participation in this study:

1. Prior treatment with an anti-PD-1, anti-PD-L1, anti-PD-L2 antibody, or any other antibody or drug specifically targeting T-cell costimulation or immune checkpoint pathways, except anti-CTLA4 antibody.
2. Subjects who have not recovered to Common Terminology Criteria for Adverse Events (CTCAE) v4.0 Grade 1 or better from the adverse events due to previous cancer therapy.
3. Evidence for an active, known or suspected autoimmune disease. Subjects diagnosed with vitiligo, type I diabetes mellitus, residual hypothyroidism due to autoimmune condition only requiring hormone replacement, psoriasis not requiring systemic treatment, or conditions not expected to recur in the absence of an external trigger are permitted to enroll.
4. Treatment with corticosteroids in an increasing dosage in the 7 days prior to the first administration of nivolumab. (A stable or decreasing dosage of  $\leq$  4 mg dexamethasone or equivalent is allowed. In addition, inhaled or topical steroids and adrenal replacement doses are permitted in the absence of active autoimmune disease.)
5. Previous malignancies (except non-melanoma skin cancers, in situ bladder cancer, gastric or colon cancers, cervical cancers/dysplasia or breast carcinoma in situ) unless a complete remission was achieved at least 1 years prior to study entry and no additional therapy is required or anticipated to be required during the study period.
6. A severe hypersensitivity reaction to prior treatment with a monoclonal antibody, or known hypersensitivity to study drugs components.
7. A positive test for hepatitis B virus surface antigen (HBV sAg) or hepatitis C virus ribonucleic acid (HCV antibody) indicating acute or chronic infection.
8. Known history of testing positive for human immunodeficiency virus (HIV) or known acquired immunodeficiency syndrome (AIDS).
9. Any serious or uncontrolled medical disorder or active infection that, in the opinion of the investigator, may increase the risk associated with study participation, study drug administration, or would impair the ability of the patients to receive protocol therapy.
10. A known psychiatric or substance abuse disorder that could interfere with cancer therapy.
11. Women of childbearing potential with a positive serum or urine pregnancy test (minimum sensitivity 25 IU/L or equivalent units of HCG) within 24 hours prior to the start of nivolumab.
12. Breastfeeding women.
13. Inability to comply with other requirements of the protocol.

#### 5.4 Sample size calculation

The total sample size of the study is 15 patients at maximum. A maximum of 5 patients will participate in phase one and 10 patients will participate in phase two. With an expected accrual rate of 1-2 patients per month, the intervention part of the study could be completed within 12 months.

### 6. TREATMENT OF SUBJECTS

#### 6.1 Investigational product/treatment

The intervention of this study is a  $[^{18}\text{F}]$ PD-L1 PET scan. The radiolabeled PET tracer  $[^{18}\text{F}]$ PD-L1 is developed by Bristol-Myers Squibb and will be produced in our center according to GMP guidelines. For additional data about the precursor material and preclinical data of the tracer we refer to the investigators brochure, version 1, 14 Dec 2015.

#### 6.2 Use of co-intervention

##### *Corticosteroids*

The use of systemic corticosteroids at baseline and during nivolumab therapy, should be avoided because of their potential interference with the pharmacodynamic activity and efficacy of nivolumab. A stable or decreasing dosage of  $\leq 4$  mg dexamethasone or equivalent is allowed. In addition, inhaled or topical steroids and adrenal replacement doses  $> 4$  mg daily dexamethasone equivalents in the absence of active autoimmune disease are permitted.

##### *Contraception methods*

WOCBP and men with reproductive potential must be willing to practice acceptable methods of birth control during the study. "WOCBP" is defined as any female who has experienced menarche and who has not undergone surgical sterilization (hysterectomy or bilateral oophorectomy) or who is not postmenopausal. Menopause is defined clinically as 12 months of amenorrhea in a woman over 45 in the absence of other biological or physiological causes. In addition, women under the age of 55 must have a documented serum follicle stimulating hormone (FSH) level greater than 40 mIU/mL.

WOCBP should use an adequate method to avoid pregnancy for 23 weeks (30 days plus the time required for nivolumab to undergo five half-lives) after the last dose of investigational drug. Men who are sexually active with WOCBP must use any contraceptive method with a failure rate of less than 1% per year. Men receiving nivolumab and who are sexually active with WOCBP will be instructed to adhere to contraception for a period of 31 weeks after the last dose of investigational product.

**7. INVESTIGATIONAL PRODUCT**

See concept IMPD attached for PET radiotracer [F]PD-L1, version 2.0, date 17-05-2016.

## 8. NON-INVESTIGATIONAL PRODUCT

### 8.1 Name and description of non-investigational product(s)

See section 3.1, page 20, of the investigators brochure for nivolumab.

### 8.2 Summary of findings from non-clinical studies

See section 4, page 21-29, of the investigators brochure for nivolumab.

### 8.3 Summary of findings from clinical studies

See section 5, page 29-88, of the investigators brochure for nivolumab.

### 8.4 Summary of known and potential risks and benefits

For efficacy and safety results of previous clinical studies, see section 5.4 and 5.5 of the investigators brochure for nivolumab.

### 8.5 Description and justification of route of administration and dosage

See section 3.2.1, page 20, of the investigators brochure for nivolumab.

### 8.6 Dosages, dosage modifications and method of administration

See section 5.2 of this clinical trial protocol for a description of dose calculation and modification for nivolumab.

### 8.7 Preparation and labelling of Non Investigational Medicinal Product

See section 3.2.2., page 20-21, of the investigators brochure for nivolumab.

### 8.8 Drug accountability

See section 3.2.3., page 21, of the investigators brochure for nivolumab for recommended storage and use conditions.

## 9. METHODS

### 9.1 Primary study parameter/endpoint

Phase one concerns the pharmacokinetic sub-study to assess the dynamics and kinetics of the PD-L1 tracer as measured by PET imaging in patients with inoperable melanoma treated with a PD1 immune checkpoint inhibitor (nivolumab). For assessment of the tracer pharmacokinetics and optimum time for scanning, serial whole body PET scans will be acquired at baseline and six weeks after treatment initiation in these patients in order to determine the tracer kinetics in major organs. Phase two will assess the association between PD-L1 expression on PET scan and PD-L1 expression on IHC.

For detailed information on study procedures, including scan sequences, we refer to paragraph 8.6 of this protocol.

### 9.2 Secondary study parameters/endpoints

Heterogeneity of tracer uptake between separate tumor lesions will be determined both for separate lesions within one patient (intra-patient heterogeneity) and for lesions in different patients (inter-patient heterogeneity).

Differences in PD-L1 expression, both assessed by PET scanning and IHC, between baseline and after 6 weeks of treatment with a PD1 immune checkpoint inhibitor will be correlated to response to treatment as measured by standard of care radiological response assessment.

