## 11. STATISTICAL ANALYSIS

This is an exploratory, feasibility study that serves to provide base case statistics for further prospective research. Primarily descriptive statistics will be used. Demographic and baseline characteristics will be summarized using means, standard deviations, medians, and ranges for continuous variables, and proportions for categorical variables. The PET results will be both qualitatively and quantitatively assessed in 15 patients. Categorical data will be assessed using the Fisher's exact test. Continual data (paired and unpaired) will be assessed using non-parametrical tests (i.e. Mann-Whitney U test and Kruskall-Wallis test).

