### 11.2 Secondary study parameter(s)

Heterogeneity between tracer uptake of separate tumor lesions will be determined. For this purpose the absolute difference in SUV between the two PET scans will be determined for all separate lesions and will be visualised in a table. Heterogeneity of this absolute difference in SUV will be analysed for

lesions in one patient (intra-patient heterogeneity) and for lesions between patients (inter-patient heterogeneity).

Although the study population is too small to generate statistical relevant information, the ability of PD-L1 expression to predict response to anti-PD1 treatment will be assessed as a secondary parameter. For this purpose the different lesions identified on the first PET-CT scan, will be qualitatively scored as responding (stable disease, partial or complete regression) or non-responding (progressive disease) according to the RECIST 1.1 criteria. The measured response will then be correlated to the absolute increase in SUV between the two PET scans for PD-L1 expression on PET and response will be correlated to the difference in immunohistochemical score for PD-L1 expression in tumor tissue samples.

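### The secondary objective needs between- and within-patient variability in uptake, but 9.2 and 11.2 name no estimator that separates them, and 11.2 analyses the change in SUV instead

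*Combined protocol and SAP*

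**What the plan says.** Section 3.2 gives the secondary objective: "To characterize between-subject and within-subject variability in accumulation" of the tracer in melanoma and NSCLC metastases. These are two separate sources of variation, and the quantity is uptake.

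Section 9.2 turns this into an endpoint. Heterogeneity of uptake between tumour lesions is to be determined "for separate lesions within one patient (intra-patient heterogeneity) and for lesions in different patients (inter-patient heterogeneity". It gives no formula.

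Section 11.2 states the analysis. First, "the absolute difference in SUV between the two PET scans will be determined for all separate lesions and will be visualised in a table". Then: "Heterogeneity of this absolute difference in SUV will be analysed for" "lesions in one patient (intra-patient heterogeneity) and for lesions between patients (inter-patient heterogeneity". No statistic, model or estimator is named.

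Section 11 sets the general approach: "Primarily descriptive statistics will be used". For continuous data it adds that they "will be assessed using non-parametrical tests (i.e. Mann-Whitney U test and Kruskall-Wallis test". Pearson or Spearman correlation appears in section 11.1, for the PET–IHC association only.

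Section 11.1 calculates SUV for all predefined regions of interest at baseline, and at week 6 for all baseline lesions plus any new ones. It sets no limit on lesions per patient.

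**The concern.** There are two gaps between the objective and the analysis.

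The first is the unit. Sections 9.2 and 11.2 both describe the inter-patient part in terms of lesions that belong to different patients. Two such lesions differ because the patients differ and also because lesions differ within any patient. A spread calculated over them contains both sources. If patients did not differ at all, this figure would still equal the intra-patient one. Patients with many lesions would also weigh more in any pooled figure.

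The second is the variable. The objective and 9.2 concern how much tracer accumulates. Section 11.2 analyses how much SUV changes between the two scans.

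The rationale of the study (section 2.4) is heterogeneity of PD-L1 expression across metastases. How much of that variation lies between patients, and how much between lesions of one patient, bears on how far a single biopsied lesion can stand for a patient. Section 11 also says the study is meant to supply starting figures for later research, so the two variance estimates are a product of the trial even though it is exploratory.

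**Working it through.** **Inputs from the documents.** At most 5 patients in phase one and 10 in phase two, 5 + 10 = 15 (section 5.4). The objective stands under phase two in section 3.2, while section 11 assesses PET results in 15 patients, so both 10 and 15 are used below. The documents give no SD, ICC or lesion count, so there is no figure of the plan to reproduce.

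**Assumptions.** ICC 0.2, 0.5 or 0.8; 3 or 5 lesions per patient.

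**Model.** Lesion value = overall mean + patient effect (variance σb²) + lesion effect (variance σw²), with ICC = σb² / (σb² + σw²).

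**Spread over lesions from different patients.** Its variance is σb² + σw² = σb² / ICC. The ratio of this SD to the between-patient SD is therefore 1/√ICC:

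- ICC 0.2: 1/√0.2 = 2.24
- ICC 0.5: 1/√0.5 = 1.41
- ICC 0.8: 1/√0.8 = 1.12

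**SD of patient means, the natural alternative.** With m lesions per patient the variance ratio to σb² is [ICC + (1 − ICC)/m] / ICC. At ICC 0.2 and m = 3 this is (0.2 + 0.8/3)/0.2 = 2.33, an SD ratio of √2.33 = 1.53. With m = 5 the variance ratio is 1.8. At ICC 0.5 it is 1.33 (m = 3) or 1.2 (m = 5), and at ICC 0.8 it is 1.08 or 1.05. Averaging reduces the overstatement but does not remove it.

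**Simulation.** 5,000 runs per setting, normal data, equal lesion counts, total variance 1.

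- The pooled lesion variance averaged 0.93 to 0.99. It falls slightly below 1 because lesions of one patient are correlated, so 1/√ICC is a slight overstatement in samples this small.
- The estimator (between-patient mean square − within-patient mean square)/m averaged 0.20, 0.50–0.51 and 0.79–0.80 for true σb² of 0.2, 0.5 and 0.8.
- The pooled within-patient variance averaged 0.79–0.80, 0.50 and 0.20 for true σw² of 0.8, 0.5 and 0.2. An ordinary pooled within-patient SD therefore serves the intra-patient part.

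Median 95% limits for the ICC:

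| Patients | Lesions each | True ICC 0.2 | True ICC 0.5 | True ICC 0.8 |
|---|---|---|---|---|
| 10 | 3 | 0.00–0.63 | 0.11–0.82 | 0.53–0.94 |
| 10 | 5 | 0.00–0.56 | 0.21–0.79 | 0.58–0.93 |
| 15 | 3 | 0.00–0.54 | 0.18–0.76 | 0.59–0.92 |
| 15 | 5 | 0.01–0.48 | 0.26–0.74 | 0.63–0.91 |

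**The tests in section 11.** Kruskal-Wallis with patient as the group can show that patients differ in location, but not by how much. On one simulated data set its p-value was the same (3.4 × 10⁻⁵) after every value was multiplied by 10.

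**Uptake against change.** If every lesion kept its baseline SUV to week 6, all differences would be zero and the analysis in 11.2 would show no heterogeneity, however much uptake varied between lesions or patients. The spread of change therefore cannot stand in for the spread of uptake.

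**The case against.** The strongest reply is that the plan attaches no statistic to inter-patient heterogeneity. The wording in 9.2 and 11.2 is loose, the objective itself says between-subject, and a competent analyst could separate the sources without being told. This stands in part. A reader might infer that the plan defines inter-patient heterogeneity as the pooled lesion spread and is bound to report a wrong number. The documents do not support that. They leave the estimator open, and the literal reading is one that can go wrong.

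A reader might also infer that the trial could not tell patient differences from lesion differences. That does not follow. If the pooled and the intra-patient variances are both reported, their difference approximates σb², and a Kruskal-Wallis test by patient speaks to whether patients differ. What remains is that the figure labelled inter-patient would not itself be the between-subject variability, and that under 11.2 the figures would describe change.

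Nor do the documents make the rank tests the measure of heterogeneity. Section 11 lists them for continuous data in general, after stating a mainly descriptive approach, so there is no case for removing them.

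Finally, a reader might take the inflated variance to distort later sample sizes by 1/ICC. This fails. A later patient-level comparison that averages m lesions per patient needs σb² + σw²/m, and with one lesion that is the pooled quantity itself. Planning on σb² alone would undersize such a study. The useful product is both components, from which the variance for any m follows.

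The point that this is a secondary aim of a small feasibility study also stands, and it limits the severity.

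**Conclusion.** The concern holds as a mismatch between the objective and its analysis. The lesion-level wording with no named estimator, together with the use of change in SUV, would not by itself deliver the between- and within-subject variability in uptake that section 3.2 promises.

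On the literal reading the between-patient SD can be overstated about 2.2-fold if lesions within a patient are only weakly alike, and by little more than a tenth if they are strongly alike. These sizes rest on a one-way random-effects model and on assumed ICCs. The intra-patient part is not at risk if a pooled within-patient SD is used. The mismatch between uptake and change needs no assumption, because it can be read directly from sections 3.2, 9.2 and 11.2. Severity is minor to moderate.

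**What to change.** In sections 9.2 and 11.2:

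1. State that the secondary objective is addressed with lesion SUV at baseline and, separately, at week 6.
2. For each visit, fit log(SUV) of all lesions with a random intercept for patient by REML, which also handles unequal lesion counts. Report the between-patient SD, the within-patient SD and the ICC, each with a 95% interval.
3. Add a dot plot of lesion values by patient. Mark tumour type on it or include it as a fixed effect, so that a melanoma–NSCLC difference is not counted as between-patient variation.
4. If the change in SUV is kept, present it as a separate quantity with the same model. Use unlogged differences or log ratios, because a signed difference cannot be logged.

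The cost is a few sentences of analysis text and one simple model per visit, on data the study already collects. The drawback is imprecision: with at most 15 patients the intervals will be wide, and at a low ICC the lower limit will often sit at or near zero. The plan should say so in advance.
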